6.5.2. Study Conduct and Patient Disposition

The following analyses will be performed based on the FAS overall and separately by treatment group.

6.5.2.1. Patient Disposition

For randomized cohorts

The percentages below will be calculated based on the number of patients in the FAS.

- Total number of patients screened overall;
- Number of patients who discontinued from the study prior to randomization overall and by the main reason for discontinuation;
- Number and percentage of randomized patients in each of the analysis sets defined in [Section 4](#);
- Number and percentage of randomized patients with study drug ongoing (separately for each study drug when administered in combination);
- Number and percentage of randomized patients who discontinued study drug overall and by the main reason for discontinuation of study drug (separately for each study drug when administered in combination);
- Number and percentage of patients who entered follow-up;
- Number and percentage of patients who discontinued the study overall and by the main reason for discontinuation.

The results of the randomization algorithm (according to IRT) will be summarized as follows:

- Number and percentage of randomized patients overall, by region (Europe, EEA (required by EudraCT), North America, Latin America, Middle East, Asia, Australasia, Africa), by country within region;
- Number and percentage of randomized patients by center;
- Cross tabulation: patients randomized (Arm A/Arm B/none) vs. patients treated (Arm A/Arm B/none).

For non-randomized cohorts

The percentages below will be calculated based on the number of patients in the FAS.

- Total number of patients screened overall.
- Number of patients who discontinued from the study prior to treatment with study drug overall and by the main reason for discontinuation.
- Number and percentage of treated patients in each of the analysis sets defined in [Section 4](#).
- Number and percentage of patients with study drug ongoing (separately for each study drug when administered in combination).
- Number and percentage of patients who discontinued study drug overall and by the main reason for discontinuation of study drug (separately for each study drug when administered in combination).
- Number and percentage of patients who entered follow-up.
- Number and percentage of patients who discontinued the study overall and by the main reason for discontinuation.

In addition the following will be summarized:

- Number and percentage of treated patients overall, by region (Europe, EEA (required by EudraCT), North America, Latin America, Middle East, Asia, Australasia, Africa), by country within region.
- Number and percentage of treated patients by center.

6.5.2.2. Protocol Deviations

All protocol violations that impact the safety of the patients and/or the conduct of a study and/or its evaluation will be reported. These include:

- Patients who are dosed on the study despite not satisfying the inclusion criteria;
- Patients who develop withdrawal criteria whilst on the study but are not withdrawn;
- Patients who receive the wrong treatment or an incorrect dose;
- Patients who receive an excluded concomitant medication;
- Deviations from GCP.

The identification of these and other CSR-reportable deviations will be based on the inclusion/exclusion criteria or other criteria presented in the protocol.

6.5.3. Study Treatment Compliance and Exposure

The following analyses will be based on the safety analysis set by treatment group.

Cycle definitions for study drugs that are administered in combination apply to all the study drugs in the combination. I.e., cycle is patient-dependent, rather than study-drug-dependent when study drugs are administered in combination.

For Cycle X, actual cycle start date for each patient is

- the earliest start date of dosing in the Cycle X day 1 visit CRF exposure page, if the patient received study treatment on that visit (ie, any study drug with dose>0 at that visit).
- the first day of assessments in the Cycle X day 1 visit, if the patient did not receive study treatment on that visit (ie, all study drugs had dose=0 at that visit). Use start date in the exposure page if available; if start date is not available then use date of collection of vital signs on Cycle X day 1 visit.

Actual cycle end date for each patient is,

- for all cycles X except the last cycle, actual cycle end date = actual cycle (X+1) start date – 1 day;
- for the last cycle, actual cycle end date = actual cycle start date + 28 days – 1 day.

Cycle duration (weeks) = (actual cycle end date – actual cycle start date + 1)/7.

When summarizing exposure for each study drug, only cycles from first dose of study treatment until the last cycle with non-zero dose of at least one of the study drugs should be included.

Exposure may be summarized (overall) as dose received (cumulative dose, actual dose intensity) and as dose received relative to intended dose (relative dose intensity [RDI]).

The information that will be summarized depends on how the study drug is dosed (eg, infusion cyclical, oral daily, oral cyclical).

The formulae below should be applied to each study drug separately even when study drugs are administered in combination.

The derivations below are provided assuming 1 cycle = 4 weeks and for the following study drugs (administered alone or in combination):

- PF-05082566 administered as a 1-hour IV infusion (mg/kg) once every 4 weeks in 4-week cycles.

- Rituximab administered as a 1-hour IV infusion at a fixed dose of 375 mg/m² once every week (Day -7, Day 0, Day 7, Day 14) for the first cycle of treatment.

6.5.3.1. Exposure to PF-05082566

The dose level for PF-05082566 is calculated as actual dose administered/weight (mg/kg). The last available weight of the patient on or prior to the day of dosing will be used.

Intended duration of treatment with PF-05082566 (weeks) =

$$(\text{end date} - \text{date of first dose of PF-05082566} + 1) / 7,$$

where end date = start date of last cycle with non-zero dose of PF-05082566 + 28 – 1.

Duration of exposure to PF-05082566 (weeks) =

$$(\text{last dose date of PF-05082566} - \text{first dose date of PF-05082566} + 28) / 7.$$

Cumulative dose overall is the sum of the actual doses of PF-05082566 received overall.

Actual Dose Intensity (DI)

- Overall actual DI (mg/kg/4-week cycle) = [overall cumulative dose (mg/kg)] / [intended duration of treatment with PF-05082566 (weeks)/4].

Relative Dose Intensity (RDI)

- Intended DI (mg/kg/4-week cycle) = [intended cumulative dose per cycle] / [intended number of 4-weeks in a cycle] = [d (mg/kg)] / [1 (4-week cycle)] = d (mg/kg/4-week cycle).
- Overall RDI (%) = 100 × [overall actual DI] / [intended DI]
= 100 × [overall actual DI] / [d (mg/kg/4-week cycle)].

where d ranges from 0.006 mg/kg to 10 mg/kg (see [Section 3.7.1](#)).

6.5.3.2. Exposure to Rituximab

The dose level for rituximab is calculated as actual dose administered/BSA (mg/m²). The last available BSA of the patient on or prior to the day of dosing will be used.

Intended duration of treatment with rituximab (weeks) = 4 weeks

Duration of exposure to rituximab (weeks) =

$$(\text{last dose date of rituximab} - \text{first dose date of rituximab} + 7) / 7.$$

Cumulative dose overall is the sum of the actual doses of rituximab received overall.

Actual Dose Intensity (DI)

- Overall actual DI ($\text{mg}/\text{m}^2/4\text{-week cycle}$) = [overall cumulative dose (mg/m^2)] / [intended duration of treatment with rituximab (weeks)/4].

Relative Dose Intensity (RDI)

- Intended DI ($\text{mg}/\text{m}^2/4\text{-week cycle}$) = [intended cumulative dose per cycle] / [intended number of 4-weeks in a cycle] = $[375 \times 4 (\text{mg}/\text{m}^2)] / [1 (4\text{-week cycle})] = 375 \times 4 (\text{mg}/\text{m}^2/4\text{-week cycle})$.
- Overall RDI (%) = $100 \times [\text{overall actual DI}] / [\text{intended DI}]$
= $100 \times [\text{overall actual DI}] / [375 \times 4 (\text{mg}/\text{m}^2/4\text{-week cycle})]$.

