21. In Portion B only, patients may have received additional doses of rituximab (375 mg/m²) starting at Cycle 4, in accord with the local and institutional Standard of Care, and at the discretion of the investigator. A single dose of rituximab will be administered on Day 0 starting on Cycle 4 and will be repeated every 2 cycles up to a maximum of 4 additional doses (up to Cycle 10 Day 0).
22. Tumor Assessments: Tumor assessments will include all known or suspected disease sites. Imaging may include chest, abdomen and pelvis CT or MRI scans. Brain scans and will be performed at baseline for patients with CNS disease or if disease is suspected, and on study as appropriate to follow disease. Baseline CNS imaging is not required unless to confirm stability of existing CNS metastases or for symptomatic patients to rule out CNS metastases. Bone scans will be performed at baseline if disease is suspected only for patients enrolled in Portion A, and on study (every 16 weeks ±1 week) as appropriate to follow disease. CT or MRI scans to be done once every 8 weeks (±1 week) for the first 10 months on study treatment, then subsequently every 16 weeks (±1 week) until objective disease progression. Confirmation of response (CR/PR) should be done at least 4 weeks after the initial response, per RECIST v1.1 CCI. Confirmation of response (CR/PR) is not required for patients with NHL per Cheson 2007 response criteria. Tumor assessment should be repeated at the end of treatment visit if more than 6 weeks have passed since the last evaluation. Patients whose disease has not progressed at the end of treatment will enter into disease follow-up. During this follow-up period, patients will have disease assessments performed every 16 weeks (±1 week). All radiographic images from patients with rituximab refractory FL enrolled in the expansion cohorts Portion B must be collected and sent to a central radiology laboratory for potential future independent review. See the study manual for more details

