6.5.3.4. Dose Delays

Applicable to PF-05082566 and rituximab.

Dose Delay is the difference between the actual time between two consecutive non-zero doses and the planned time between the same two consecutive non-zero doses.

PF-05082566 in Portion A

Dose delay in Cycle x (days) = Date of first dose of PF-05082566 in Cycle x – Date of first dose of PF-05082566 in Cycle (x-1) – 28, where $x > 1$.

PF-05082566 in Portion B

In Cycle 1,

Dose delay (days) = Study day of first dose of PF-05082566 – 9 [Note: Cycle 1 starts on Day -7 and the first dose of PF-05082566 is scheduled for Cycle 1 Day 1].

In Cycle x,

Dose delay in Cycle x (days) = Date of first dose of PF-05082566 in Cycle x – Date of first dose of PF-05082566 in Cycle (x-1) – 28, where $x > 1$.

Rituximab

Dose delay for Dose x (days) = Date of Dose x – Date of Dose (x-1) – 7, where $x > 1$.

Dose delays will be grouped into the following categories:

- No delay.
- 1-2 days delay.
- 3-6 days delay.
- 7 or more days delay.

For example, for PF-05082566, administered on a 4-week schedule, if one patient receives PF-05082566 on Day 1, then the next PF-05082566 administration date will be on Day 29; however, if the patient receives PF-05082566 at Day 30 or 31, this will be summarized in the 1-2 days delay category.

The number and percentage of patients with delayed study drug administration and maximum length of delay, ie, the worst case of delay if patients have multiple dose delays will be summarized.

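### For Portion B patients given the later rituximab doses that Amendment 9 removed, the SAP exposure formulas return a relative dose intensity of 125–200% and false delays of 49–63 days

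*SAP*

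**What the plan says.** SAP Section 6.5.3 describes the rituximab regimen behind its derivations as "once every week (Day -7, Day 0, Day 7, Day 14) for the first cycle of treatment". It also says that exposure summaries run through the last cycle in which either study drug was given at a non-zero dose.

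SAP Section 6.5.3.2 then sets:

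- the denominator: "Intended duration of treatment with rituximab (weeks) = 4 weeks";
- the numerator: "Cumulative dose overall is the sum of the actual doses of rituximab received overall";
- the intended dose intensity: 375 x 4 mg/m² per 4-week cycle.

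SAP Section 6.5.3.4 defines a delay as the actual interval between two doses minus "the planned time between the same two consecutive non-zero doses". For rituximab it turns this into "Date of Dose x – Date of Dose (x-1) – 7" for every dose after the first. Each patient's worst delay is reported, and the top category is 7 or more days.

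On the protocol side, Table 5 footnote 21 says that in Portion B "patients may have received additional doses of rituximab" from Cycle 4. These were single 375 mg/m² doses on Day 0, repeated every two cycles, with at most four extra doses (to Cycle 10 Day 0). The document history shows that Amendment 9 removed this re-treatment. Sections 5 and 5.4 now give rituximab in Cycle 1 only.

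**The concern.** The numerator and denominator of the rituximab dose intensity cover different periods. Doses from Cycle 4 onwards raise the cumulative dose, but the intended duration stays at 4 weeks and the intended dose at four administrations. The PF-05082566 formula in SAP Section 6.5.3.1 avoids this, because its intended duration runs to the last cycle dosed.

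The delay formula has a related fault. It treats 7 days as the planned gap between any two rituximab doses, including gaps that were planned at 8 or 10 weeks.

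At stake is the description of treatment in the affected Portion B groups. The 14 expansion patients enrolled as of September 2016 (10 FL, 4 DLBCL) were all treated at 1.2 mg/kg, so any distortion from them falls in one row of the exposure tables. That row could show rituximab above plan and long delays for patients treated as the protocol then allowed. A genuine delay in Cycle 1 would be replaced in the worst-delay summary by the artificial one.

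**Working it through.** **Inputs**

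- Cycle 1 doses on Days -7, 0, 7 and 14 (SAP 6.5.3).
- Dose per infusion 375 mg/m²; intended duration 4 weeks; intended dose intensity 375 x 4 = 1500 mg/m² per 4-week cycle (SAP 6.5.3.2).
- Extra doses on Day 0 of Cycles 4, 6, 8 and 10 (protocol Table 5 footnote 21).
- Cycle length 28 days (protocol Table 5 footnote 19).

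**Day axis.** Cycle k Day 1 falls on day 1 + 28(k - 1), and Day 0 is the day before. The extra doses therefore fall on days 84, 140, 196 and 252. As a check, counting Day -7 as study day 1 puts Cycle 1 Day 1 on study day 9. This matches the 9 that SAP 6.5.3.4 subtracts for the first PF-05082566 dose in Portion B.

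**Formulas, for n full doses**

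- RDI = 100 x [n x 375 / (4/4)] / 1500
- Delay = date of dose x - date of dose (x - 1) - 7
- Duration of exposure (weeks) = (last dose date - first dose date + 7) / 7

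**The plan's own case first.** With four weekly doses, RDI = 100 x 1500 / 1500 = 100%, the delays are 0, 0 and 0, and the duration is (14 + 7 + 7)/7 = 4 weeks. The formulas work for the regimen they assume.

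**With extra doses, all full and on schedule**

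| Extra doses | Total mg/m² | RDI | Calculated delays for extra doses (days) | Duration (weeks) |
|---|---|---|---|---|
| 1 | 1875 | 125% | 63 | 14 |
| 2 | 2250 | 150% | 63, 49 | 22 |
| 3 | 2625 | 175% | 63, 49, 49 | 30 |
| 4 | 3000 | 200% | 63, 49, 49, 49 | 38 |

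The 63 comes from 84 - 14 = 70 days, less 7. The 49 comes from 56 days, less 7. Visit windows move these by a few days.

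**The same doses under the SAP's general definition.** The planned intervals are 7, 7, 7, 70 and then 56 days. Actual minus planned is 0 for every dose.

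**Consequence for the worst-delay table.** Each patient re-treated on schedule has a maximum of at least 63 days and falls in the 7-or-more-days category, whatever happened in Cycle 1.

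**Offsetting in RDI.** Three of the four Cycle 1 doses plus one re-treatment dose is 4 x 375 = 1500 mg/m², so RDI is 100% although a Cycle 1 dose was missed.

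**Group level.** Each extra full dose adds 25 points to one patient's RDI. A group mean over N patients therefore rises by 25 x (total extra doses) / N. The documents do not give the total, so the group shift cannot be computed.

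**The case against.** The best defence is that SAP 6.5.3 names the regimen its derivations assume, and that the treatment groups are labelled as four weekly rituximab doses. On that reading, later discretionary doses simply lie outside the formulas. This stands as a statement of intent, but no sentence excludes those doses. The cumulative dose is defined without a Cycle 1 limit, the cycles included run to the last dose of either drug, and the subtraction of 7 days applies to every dose after the first. A programmer following the text would include them.

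Other objections hold and limit the point:

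- **Re-treatment has ended.** A reader might infer from the future tense in part of footnote 21 that all of the up to 100 FL patients are affected. Amendment 9 and protocol Sections 5 and 5.4 do not support that.
- **The extra doses were real.** A reader might see an RDI above 100% as over-dosing. It reflects doses the protocol then allowed, set against a denominator that omits them. The duration-of-exposure summary would give a clue to this.
- **Masking is narrow.** A reader might infer that Cycle 1 under-dosing is generally hidden. Partial doses below 90% of plan are counted in SAP 6.5.3.3, and infusion interruptions in SAP 6.5.3.6. Under protocol Section 5.4, a patient whose rituximab infusion after Cycle 1 Day 1 cannot be completed within 24 hours leaves study treatment. What can be offset in RDI is mainly a wholly omitted dose in a patient who still reached Cycle 4.
- **Nothing inferential depends on this.** The tables are descriptive and no hypothesis test is planned. The DLT window is the first two cycles, before any re-treatment.

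**Conclusion.** For re-treated Portion B patients the stated rules give wrong results: RDI of 125 to 200%, and calculated delays of 63 days and then 49 days where the true delay is zero. The rituximab delay formula also contradicts the general definition in the same section. The worst-delay summary is the more serious half, because it misclassifies every patient re-treated on schedule and overwrites any real Cycle 1 delay. RDI can also offset a wholly omitted Cycle 1 dose.

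The effect is confined to descriptive exposure tables and to an early subset whose number the documents do not state. The 14 expansion patients of September 2016 are a dated enrolment count. They are neither the number re-treated nor an upper bound, since Amendment 9 is dated 06 January 2017. To be affected, a patient had to reach Cycle 4 and, where re-treatment was optional, the investigator had to choose it. The 200% figure needs all four extra doses. All figures assume full doses given on the scheduled days. The point is worth correcting before the tables are programmed, but it does not bear on response, survival or DLT results.

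**What to change.** In SAP 6.5.3.2 and the rituximab part of 6.5.3.4, restrict cumulative dose, dose intensity, RDI, duration of exposure and dose delay to doses given in the Cycle 1 course. Select these doses by Cycle 1 visit, not by taking the first four. Otherwise a Cycle 4 dose would stand in for a missed Cycle 1 dose, and the one repeat infusion allowed by Table 5 footnote 4 could push out a scheduled dose.

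List or summarise later rituximab doses separately, by number of patients and number of doses. If delays are reported for them, measure against the interval planned at the time: 70 days from Cycle 1 Day 14 to Cycle 4 Day 0, then 56 days. On-schedule dosing then gives an RDI of 100% and delays of 0.

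The cost is a few sentences in the SAP and minor programming. No data collection or protocol change is needed.

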6.5.3.3. Dose Reductions

Applicable to PF-05082566 and rituximab.

Dose reduction is defined as actual non-zero dose < 90% of the planned dose.

The number and percentage of patients with at least one dose reduction as well as a breakdown of the number of dose reductions (1, 2, 3, ≥ 4) will be summarized.

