23. AE Assessment: AEs should be documented and recorded at each visit using NCI CTCAE version 4.03. Patients must be followed for AEs for 28 days after the last treatment administration or until all drug related toxicities have resolved, whichever is later; or earlier than 28 days should the patient commence another anticancer therapy in the meantime. For SAEs, the active reporting period to Pfizer or its designated representative begins from the time that the patient provides informed consent, which is obtained prior to the patient’s participation in the study, ie, prior to undergoing any study related procedure and/or receiving investigational product, through and including 60 calendar days after the last administration of the investigational product. SAEs experienced by a patient after the active reporting period has ended should be reported to

the Sponsor if the investigator becomes aware of them; at a minimum, all SAEs that the investigator believes have at least a reasonable possibility of being related to study drug are to be reported to the Sponsor.

24. Concomitant Medications: All concomitant medications including supportive care drugs (eg, Anti emetic treatment and prophylaxis), and the drugs used to treat AEs or chronic diseases should be recorded in the CRF.

CCI

30. Central Histopathology Review of FL Diagnosis (Portion B only): Slides from the archival (tissue collected within the last 6 months) OR a baseline (tissue collected *de novo* during the screening period prior to the first dose of PF-05082566) tumor biopsy must be sent to a central pathology laboratory for independent review. Confirmation of the FL diagnosis is not required for patient enrollment. See the study manual for more details.

CCI

32. Bone marrow (BM) biopsy or aspirate: Required for patients with potential CR by radiological assessments to determine the response category.

Table 6. Schedule of Activities: Portion A (PF-05082566 Alone: Dose Expansion Cohorts): Pharmacokinetic assessments

Assessments [(±) 2 days for cycles >1]	Cycle 1			Cycle 2 and 3	Cycle 4			Cycle ≥5	End of Treatment	
	Day 1	Day 7	Day 14	Day 1	Day 1	Day 7	Day 14	Day 1		
Blood for PF-05082566 PK ¹	X	X	X	X	X	X	X	X (every 4 cycles)	X	
Blood for Immunogenicity (ADA) testing ²	X			X	X			X (every 4 cycles)	X	

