PF-05082566 will be administered at 2 planned dose escalation levels (5.0 mg/kg and 10 mg/kg) by IV infusion of 1 hour (-5/+15 min) every 4 weeks. Each patient will initially receive the first dose on Cycle 1 Day 1 with a 28-day observation period. Cycle 2 Day 1 will start on Day 29. After completion of Cycle 2, patients will be asked to sign an additional consent document for confirmation of the patient's willingness to continue participation in this study before starting Cycle 3. Lower dose levels, as described above for Portion A, may be explored at any time during the study if this is clinically and scientifically warranted based on the emerging safety data in Japanese patients. Study centers will receive a notification if additional dose levels are explored.

Portion B:

PF-05082566 will be administered by IV infusion of 1 hour (-5/+15 min) every four weeks at dose levels as shown for Portion A, with the exception that the Portion B dose escalation starts at 0.03 mg/kg.

In the expansion cohort, patients enrolled in Portion B will receive a dose of PF-05082566 at 0.24 mg/kg or 1.2 mg/kg in combination with 375 mg/m² rituximab. If a PF-05082566 dose reduction is required due to the PF-05082566-related toxicity, this may be allowed as an alternative to discontinuation of treatment. No dose reduction is allowed for patients treated at the 0.24 mg/kg dose level. See [Section 5.4.4](#) for details.

Rituximab will be administered in Cycle 1 at a fixed dose of 375 mg/m², once per week for a total of 4 weeks. The first dose of rituximab will be administered on Cycle 1 Day (-7) followed by the second dose a week later on Day (0).

The first dose of PF-05082566 will be given approximately 24 hours after the second weekly, full dose of rituximab (Cycle 1 Day 1). This allows for the observance of any potential reactions to rituximab treatment prior to the initiation of PF-05082566 dosing. In this study, full dose of rituximab is defined as either the planned dose, or for those patients who develop an infusion reaction, as at least 50% of the planned dose. Continuation with protocol activities as scheduled, following administration of less than the planned rituximab dose, requires confirmation of dose acceptability from the Sponsor.

The proposed schedule and duration of infusion may be reconsidered and amended during the study based on the emerging safety and PK **CCI** data.

Duration of Treatment

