5.4.4. Dose Modifications for PF-05082566

Following dosing interruption or cycle delay due to toxicity (see [Section 5.4.2](#) and 5.4.3), the PF-05082566 dose may need to be reduced when treatment is resumed.

No specific dose adjustments are recommended for Grade 1/2 treatment-related toxicity. However, investigators should always manage their patients according to their medical judgment based on the particular clinical circumstances.

Patients experiencing recurrent and intolerable Grade 2 toxicity may resume dosing at the next lower dose level, if possible, once recovery to Grade ≤ 1 or baseline is achieved.

Patients experiencing an AE meeting the DLT definition (see [Section 3.4](#) for DLT definition) may resume dosing at the next lower dose level, if possible, once adequate recovery is achieved (see [Section 5.4.3](#)).

Dose reduction of PF-05082566 by 1 and, if needed, 2 dose levels (Table 11) will be allowed depending on the type and severity of toxicity encountered. Patients requiring more than 2 dose reductions will be permanently discontinued from the study treatment and entered into the follow-up phase. Once a patient has a dose reduction of PF-05082566 for a PF-05082566 related toxicity, the dose will not be re-escalated. All dose modifications and adjustments must be clearly documented in the patient's source notes and CRF.

Patients treated with PF-05082566 at 0.24 mg/kg requiring a dose reduction should be permanently withdrawn from study treatment.

Table 11. Available Dose Levels for PF-05082566 (mg/kg)

1.2
0.6
0.24

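### The SAP's dose-reduction rule cannot return the number of PF-05082566 level reductions, because the planned dose is undefined and the rule counts infusions rather than steps down (minor)

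*SAP*

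**What the plan says.** **Reductions.** SAP 6.5.3.3 applies one rule to PF-05082566 and rituximab: "Dose reduction is defined as actual non-zero dose < 90% of the planned dose". It reports the patients with at least one reduction, "as well as a breakdown of the number of dose reductions (1, 2, 3, ≥ 4) will be summarized". Neither that section nor the rest of SAP 6.5.3 defines the planned dose. The nearest guide is the relative dose intensity (RDI) formula in SAP 6.5.3.1, whose intended dose is the treatment-group dose d, "where d ranges from 0.006 mg/kg to 10 mg/kg".

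In Protocol 5.4.4 a dose reduction is a step down a ladder of levels (Table 11: 1.2, 0.6 and 0.24 mg/kg). Two rules bear on the count: "Patients requiring more than 2 dose reductions will be permanently discontinued from the study treatment", and "Once a patient has a dose reduction of PF-05082566 for a PF-05082566 related toxicity, the dose will not be re-escalated". Patients at 0.24 mg/kg who need a reduction are withdrawn from treatment. For the escalation cohorts, Protocol 3.3.1 adds intermediate levels of 0.45, 0.9, 1.8, 3.6 and 7.5 mg/kg.

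For rituximab, Protocol section 5 defines a full dose as the planned dose or, in patients with an infusion reaction, "as at least 50% of the planned dose".

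**Delays.** SAP 6.5.3.4 takes the interval between consecutive PF-05082566 doses minus 28 days, and sorts the result into none, 1-2, 3-6 and 7 or more days. Its example is that "if the patient receives PF-05082566 at Day 30 or 31, this will be summarized in the 1-2 days delay category". It then reports the number of patients with delayed administration and each patient's longest delay. The protocol's visit window for Day 1 is ± "2 days for cycles >1" (Table 6 header; Table 5 gives the same window for Cycle 2 onward).

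**The concern.** The protocol's reduction is an event that happens at most twice. The SAP's reduction is a state, tested at each infusion. Because a lowered dose stays lowered, the two counts agree only by accident. Two programmers could follow this SAP correctly and put the same patient in different rows, and neither row need match the clinical record.

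The rule also cannot separate a deliberate step to a lower level from an infusion stopped early. These say different things about tolerability. For rituximab, which has one fixed dose and no ladder of levels, an entry in this table would ordinarily be an incomplete infusion, including some that the protocol accepts as full doses.

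At stake is the accuracy of the exposure tables that describe how well each dose level could be kept up. The delay table has a lesser form of the same fault: its overall row mixes visits that comply with the protocol with doses that were truly late.

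**Working it through.** **Step 1: reproduce the SAP's own example.** Delay = (dosing day − 1) − 28. Day 29 gives 0, Day 30 gives 1, Day 31 gives 2 and Day 32 gives 3. The stated 1-2 day category for Days 30 and 31 is reproduced.

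**Step 2: does each level step trip the 90% rule?** Yes. 0.6/1.2 = 50% and 0.24/0.6 = 40%. The escalation intermediates give 0.45/0.6 = 0.9/1.2 = 1.8/2.4 = 7.5/10 = 75%, and 3.6/5 = 72%. A weight gain of 10% without recalculation gives 1/1.10 = 90.9%, so permitted weight drift does not trip it.

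**Step 3: count one reduction.** Take 1.2 mg/kg in Cycles 1-2 and 0.6 mg/kg from Cycle 3 to Cycle N, with no delays.

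- Planned = assigned level: each infusion from Cycle 3 is at 50% of plan, so the count is N − 2.
- Planned = dose prescribed at that visit: each infusion is at 100% of plan, so the count is 0.
- Steps down between consecutive infusions: 1.
- RDI = (2 × 1.2 + (N − 2) × 0.6) / (N × 1.2).

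| Cycles treated | Planned = assigned | Planned = prescribed at visit | Level reductions | RDI |
|---|---|---|---|---|
| 4 | 2 | 0 | 1 | 75.0% |
| 6 | 4 | 0 | 1 | 66.7% |
| 8 | 6 | 0 | 1 | 62.5% |
| 12 | 10 | 0 | 1 | 58.3% |

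At 8 cycles the RDI is (2.4 + 3.6)/9.6 = 62.5%. With two steps (two cycles each at 1.2, 0.6 and 0.24 mg/kg), the assigned-level reading counts 4; the true number is 2.

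**Step 4: compare with what is possible.** In the expansion cohorts, level reductions cannot exceed 2 from 1.2 mg/kg, 1 from 0.6 and 0 from 0.24. For PF-05082566 the rows for 3 and ≥4 therefore cannot contain numbers of level reductions.

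**Step 5: incomplete infusions.** On either reading, a non-zero infusion below 90% of plan is a reduction. A rituximab infusion of 50% to <90% after a reaction is a full dose in the protocol and a reduction in the SAP.

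**Step 6: in-window delays.** The documents give no distribution of visit days, so this step is illustrative. Assume visits uniform over −2 to +2 days around the previous dose date + 28. The chance that a given interval is 1 or 2 days long is 2/5, and over k doses P(at least one) = 1 − (3/5)^(k−1).

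| Doses | Delayed, window from previous dose | Delayed, window from fixed calendar | 3 days or more, fixed calendar |
|---|---|---|---|
| 2 | 40% | 40% | 0% |
| 3 | 64% | 76% | 12% |
| 4 | 78% | 92% | 24% |
| 6 | 92% | 99% | 44% |

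The calendar columns come from enumerating all offset sequences with Cycle 1 Day 1 held fixed, since the window starts at Cycle 2. With the window measured from the previous dose, no in-window visit reaches the 3-6 day category. For lower chances of in-window lateness per cycle, 1 − (1 − p)^5 over five intervals gives 22.6%, 41.0% and 67.2% for p = 5%, 10% and 20%.

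**The case against.** The strongest reply is that little depends on these tables, and that a sensible reader can work around them.

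- The RDI formula uses the group dose, which favours the assigned-level reading. On that reading each patient with a level reduction is correctly placed in the at-least-one row, and RDI shows the lowered exposure. This stands: only the 1/2/3/≥4 breakdown is then inflated. But the SAP does not state that reading, and on the other one both rows miss the reduction.
- The four count categories may be generic, with programmers expected to count level changes. The text does not say so. It defines a reduction by comparing a dose with a threshold.
- The delay rule is deliberate and gives 1-2 days its own category, so in-window visits can be set aside and longer delays remain visible. This largely stands. What remains is the overall row of delayed patients and, if the window is tied to a fixed calendar, the 3-6 day row.
- Reductions may be few: Protocol 1.4 reports no DLTs in 133 patients. This limits the practical size of the problem but does not make the definition right.

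A reader might go further and infer that the tables behind the RP2D are wrong, or that true differences between 0.24, 0.6 and 1.2 mg/kg will be masked. The documents support neither. Protocol 3.6 bases the RP2D on the primary and secondary endpoints, and Protocol 2.2 lists neither reductions nor delays among them. The remark in 3.6 on long-term feasibility concerns declaring the MTD as the RP2D. Reduction counts differ between dose groups by design in any case, since none is possible at 0.24 mg/kg.

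**Conclusion.** The point holds for the reduction count. As written, SAP 6.5.3.3 turns one level reduction into one count per later infusion (6 in a patient reduced at Cycle 3 and treated to Cycle 8) or into none, depending on a term it does not define. Neither reading gives the number of level reductions, and incomplete infusions are mixed in. This follows from the two documents and rests on no assumed distribution.

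The delay point is secondary. That in-window doses enter the overall delayed row is certain. The 40%, 64%, 78% and 92% of patients with 2, 3, 4 and 6 doses rest on visits uniform in a window measured from the previous dose, and would be lower if sites mostly dose on the due day. It would be too much to say that delays will look near-universal.

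Severity is minor. These are descriptive exposure and compliance tables, and no hypothesis test is planned. The DLT, adverse event, discontinuation and RDI outputs are unaffected. Any influence on dose selection is indirect, through general tolerability review such as that for the FL-3 dose (Protocol 3.1.2).

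**What to change.** **SAP 6.5.3.3.** Count a PF-05082566 dose reduction once, at the first infusion whose assigned dose level is lower than that of the previous infusion. Apply this to any protocol dose level, including the intermediate levels of the escalation cohorts; a rule limited to Table 11 would miss those. Report incomplete infusions, meaning non-zero doses below 90% of the dose prescribed at that visit, in a separate row for both drugs.

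**SAP 6.5.3.4.** Keep the 1-2 day category. For PF-05082566 from Cycle 2, leave delays within the ±2-day window out of the overall row of patients with delayed administration. State that the planned date is the previous dose date + 28 days. The first delay counted in that row is then Day 32 (3 days).

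**Cost.** SAP wording and table programming; no change to study conduct. Protocol 5.4.4 already requires dose modifications to be documented in the CRF. The CRF itself is not among the documents, so confirm that it holds the assigned level and the prescribed dose at each visit before finalising the derivation.
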